- (B) The two experimental groups, (groups A and B) will present lower craving scores in relation to the placebo group (group C will receive sham rTMS four sessions per day of intermittent theta burst, for three minutes per session, for five consecutive days, while watching a smoking video as a cue for craving) after the end of rTMS treatment,
- (C) We investigate the difference between the presentation or absence of visual cue among the two experimental groups (group A and B that will both receive real rTMS, with the difference that group B will not be presented a smoking video as cue for craving) as to whether presentation or absence of stimuli influences outcome of craving scores.

Method

Participants

Recruitment of participants will be done through public advertisements of the study, as participants belong in the healthy population. Individuals who agree to participate in this study will be volunteers. The minimum number of participants required was determined by an a priori power analysis where at least a sample size of 100 participants was suggested. (*Measures that suggested this sample size were determined by the mixed model, a small to medium effect size (0.4), at an alpha level of probability of 0.05).

Inclusion criteria of participants will be: (a) to be native speakers of the Greek language, (b) to be over the age of 18, (c) to be tobacco dependent users that wish to quit smoking.

Exclusion criteria of participants will be: (a) individuals with metallic parts inside or near the skull, (b) dependency of any other substances apart from nicotine and caffeine.

For the purposes of this study, participants will be formed into three groups. The groups will be as described below:

(A) An experimental group of 34 participants that satisfy all criteria for inclusion. This group will receive real rTMS, four sessions per day of intermittent theta burst, for three minutes per session, for five consecutive days, while watching a smoking video as a cue for craving;

(B) An experimental group of 34 participants that satisfy all criteria for inclusion. This group will receive real rTMS, four sessions per day of intermittent theta burst, for three minutes per session, for five consecutive days, with no presentation of the smoking video as a cue for craving, but a neutral video;

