(C) A control group of 34 participants that satisfy all criteria for inclusion. This group will receive sham rTMS four sessions per day of intermittent theta burst, for three minutes per session, for five consecutive days, while watching a smoking video as a cue for craving.

Design

This is a randomized, double-blind, sham-controlled study.

Procedure

Prior to the study

After advertisement of the study, potential participants will be able to contact the researcher via contact details that will be given on the advertisement. The researcher will then perform a screening interview (either by phone or email correspondence) regarding the eligibility of participants. The questions will include demographics and contact details: a) telephone number, b) email address, c) sex, d) education and occupation, e) age; and the screening will involve questions regarding eligibility: f) “how many cigarettes do you smoke per day?”, g) “for how long have you been a smoker?”, h) “has there been any period in your life that you managed to quit smoking; if yes for how long and how did you manage to do it?”, i) “are you dependant on any other substances e.g. alcohol/drugs/benzodiazepines apart from caffeine and nicotine”. These questions will be asked in Greek. If individuals meet the criteria and wish to continue, the researcher will arrange with participants details regarding their visit to the site.

At the research site

Participants will arrive at the Cyprus rTMS Centre, will receive all the required information about their participation, and if agreed, they will sign the consent form and will be led to the testing room. Participants will then complete three questionnaires on a PC, prior to the beginning of the experiment. The questionnaires are all described in Materials section and they are attached in the Appendix. All participants will undergo a breath carbon monoxide (CO) measure prior to each TMS session of each day with the use of a smokerlyzer. Further information about its use is described in the section below.

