The researcher will then take the appropriate head measures using the 10-20 system and then will place a cap on the participant's head. The participant will sit on the TMS chair and the researcher will place the (real/sham) TMS coil on the participant's left DLPFC and start the session. While participants will be receiving TMS, they will be presented with a smoking video as a cue for craving, throughout each TMS session (except for one group that they will not be presented with a cue craving video, but with a neutral video). There are two available videos, and those will be presented in a randomised manner for each participant. After each session, participants will have a forty-five minute break and then return for the next TMS session. Once done with all five days of TMS therapy, they will be again assessed with the three questionnaires.

To protect personal data and for conditions to be double-blind (participants will not know whether they receive real or sham TMS and researcher will not know whether they administer real or sham TMS), participants will be pseudo-anonymised on an excel database and will be assigned in a randomised manner to each defined group. Demographic and personal data of participants will be confidential only to the researchers involved in the study and will be protected and handled according to the Data Protection Act 2018 and the ICH Good Clinical Practice for data protection. Recorded data of participants will include: demographic details, data of self-report questionnaires at baseline and follow up measures, and CO breath levels.

Following TMS treatment

Following the end of the rTMS treatment, participants will be contacted again to complete the three questionnaires. This will be done at one week, one month and six months post-TMS treatment.

Materials

Questionnaires

The tools used in this study are three questionnaires:

- The Fagerstrom Test of Nicotine Dependence (in Greek),
- The Factor Structure of Tobacco Craving-Short Form (will be adjusted to Greek),
- The Perceived Stress Scale (in Greek).

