The data will be analysed in SPSS. Analyses of hypotheses will be carried out with a mixed model (repeated measures within and between factors). Within factors will be determined from the craving scores in the baseline and follow ups from the three questionnaires, and CO measures. Between factors will be determined by the three experimental groups. Analyses will be adjusted for sex, age and visual stimuli.

Expected outcomes & Benefits of the study

Few studies have examined smoking cessation through a TMS treatment. Further, there is a question as to whether exposure to behavioural cues before or during TMS treatment may influence craving outcomes, which may improve our understanding in the mechanisms that influence successful outcome, while using induced plasticity methods. While we expect that experimental groups will have significantly decreased craving scores compared to control group, generally this study will aid in our understanding regarding potential options for smoking cessation and possibly for other addictions with similar physiological mechanisms.

References

1. World Health Organization. (2015). WHO global report on trends in tobacco smoking 2000-2025. Geneva: WHO.
2. US Department of Health and Human Services. (2014). The health consequences of smoking—50 years of progress: a report of the Surgeon General. Atlanta, GA: US Department of Health and Human Services, Centers for Disease Control and Prevention, National Center for Chronic Disease Prevention and Health Promotion, Office on Smoking and Health, 17.
3. US Department of Health and Human Services. (2010). How tobacco smoke causes disease: What it means to you. Atlanta: US Department of Health and Human Services, Centers for Disease Control and Prevention. National Center for Chronic Disease Prevention and Health Promotion, Office on Smoking and Health.
4. European Commission (2015). Retrieved from: <https://goo.gl/1qkJFx>
5. Brody, A. L., & Cook, I. A. (2011). Manipulation of cigarette craving with transcranial magnetic stimulation. *Biological psychiatry*, 70(8), 702.
6. Goldstein, M. G., Niaura, R., Willey, C., Kazura, A., Rakowski, W., DePue, J., & Park, E. (2003). An academic detailing intervention to disseminate physician-delivered smoking cessation counseling: smoking cessation outcomes of the Physicians Counseling Smokers Project. *Preventive medicine*, 36(2), 185-196.

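### The video adjustment duplicates the group factor and is the exposure that hypothesis (C) tests, so it should not stand in the model beside group

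*Combined protocol and SAP*

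**What the plan says.** Planned Analysis specifies a repeated-measures mixed model. For the between-subject side it says: "Between factors will be determined by the three experimental groups". For the within-subject side: "Within factors will be determined from the craving scores in the baseline and follow ups from the three questionnaires, and CO measures". It then lists the adjustment: "Analyses will be adjusted for sex, age and visual stimuli". It gives no order of terms, no coding for the video variable and no list of contrasts.

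The video is set by arm. Under Participants, group A has real stimulation with the smoking video. Group B has real stimulation "with no presentation of the smoking video as a cue for craving, but a neutral video". Group C receives "sham rTMS four sessions per day of intermittent theta burst, for three minutes per session, for five consecutive days, while watching a smoking video". The procedure under At the research site agrees: the smoking video is shown throughout each session, "except for one group that they will not be presented with a cue craving video, but with a neutral video". Craving Videos describes two videos only, one smoking and one neutral.

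Two of the hypotheses at the end of the Introduction bear on this. Hypothesis (B) predicts: "The two experimental groups, (groups A and B) will present lower craving scores in relation to the placebo group". Hypothesis (C) compares A with B, both on real stimulation, "with the difference that group B will not be presented a smoking video as cue for craving".

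At the research site and Craving Videos also say that the two videos are shown in randomised fashion. That wording does not fit the arm definitions.

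**The concern.** A covariate is normally something that could differ within an arm and that one wants held constant across arms. Video is neither. Knowing a participant's group tells you the video, and the video is the only thing that separates A from B. Adjusting a group comparison for it asks for the A versus B difference with the A versus B difference removed.

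At stake is whether the model as written yields the comparisons the hypotheses name. Hypothesis (C) is the A versus B contrast, and the B part of hypothesis (B) is B versus C; the two arms in each pair saw different videos. Because the model is over-parameterised, the coefficients that appear in the output also depend on how the redundancy is resolved, and the plan does not settle that in advance.

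**Working it through.** The plan gives no figure of its own on this point, and its sample-size statement does not enter beyond the arm size. The check is on the structure of the design.

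**Inputs.** 34 participants per group (Participants); group, sex, age and video in the model (Planned Analysis); five questionnaire occasions, namely baseline, end of treatment, one week, one month and six months (Questionnaires); a carbon monoxide (CO) reading before each of 4 sessions on 5 days, so 4 × 5 = 20 (Smokerlyzer and TMS Protocol).

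| Group | Stimulation | Video |
|---|---|---|
| A | real | smoking |
| B | real | neutral |
| C | sham | smoking |

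So the smoking-video indicator equals 1 minus the indicator of group B, with no exceptions.

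**What can be estimated.** Write g for the group effects and v for the video effects (S smoking, N neutral). Apart from sex and age, the arm means are:

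- A: μ + gA + vS
- B: μ + gB + vN
- C: μ + gC + vS

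The differences between arm means are:

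- A − C = gA − gC. Video cancels, so this is estimable with video held constant.
- A − B = (gA − gB) + (vS − vN). Only the sum is estimable.
- B − C = (gB − gC) − (vS − vN). Only the sum is estimable.
- (A + B)/2 − C = (gA + gB)/2 − gC − (vS − vN)/2. Only the sum is estimable.

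The left-hand sides, which compare whole arms, are always estimable. The group parts with video held constant are not, except for A − C.

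**Degrees of freedom at one post-treatment time.** Rank of the design matrix:

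| Terms | Rank |
|---|---|
| intercept, sex, age | 3 |
| + video | 4 |
| + group | 5 |
| + group + video | 5 |

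Video given group: 5 − 5 = 0 df. Group without video: 5 − 3 = 2 df. Group given video: 5 − 4 = 1 df, and that one df is A − C.

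**Group-by-time with T occasions.** The full model has rank T (intercept and time) + 2 (group) + 2(T − 1) (group-by-time) + 2 (sex, age). That is 5 + 2 + 8 + 2 = 17 at T = 5, and 20 + 2 + 38 + 2 = 62 at T = 20. Adding video, or video and video-by-time, leaves both ranks unchanged.

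- Video as a time-constant main effect: group-by-time keeps 2(T − 1) df, which is 8 for the questionnaires.
- Video with video-by-time: T − 1 df remain, which is 4 for the questionnaires.
- Video coded as an exposure that starts after baseline: one df is lost, leaving 7 of 8 for the questionnaires.

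For CO, if all 20 readings are modelled as separate occasions, the first two cases give 38 and 19.

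**What the output would show.** Suppose redundant parameters are set to zero in order of entry, with C as the reference group. If group comes first, video is dropped and the group rows give the whole-arm differences A − C and B − C. If video comes first, B's indicator is already determined (1 minus the smoking-video indicator), so B's row is set to 0. The group rows then read A − C for A and exactly 0 for B, and A versus B taken from those rows is (A − C) − 0 = A − C. The fitted values are the same in both cases.

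**Two-factor coding.** Intercept, sex, age, stimulation and video have rank 5, the same as the group model. The stimulation effect is A − C and the video effect is A − B. Adding their interaction leaves the rank at 5, so it has 0 df: there is no sham arm with the neutral video.

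**The case against.** The strongest reply is that the harm is hypothetical. The fit does not change, every whole-arm contrast and every within-group change remains available, and on the plainest reading of the adjustment (a time-constant main effect, like sex) group-by-time keeps all 8 df. The loss of half needs a video-by-time term that the plan never mentions, and misreading a zeroed row would be an analyst's error. All of this is true, and it is why the point is not graver. It does not make the term right. Under that same reading, a group comparison adjusted for video still reduces to A versus C, and the plan fixes neither the order of terms nor the contrasts that would prevent the misreading.

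A second reply is that the videos are described as randomised. If video truly varied within arms, the single-time design would be full rank (6 columns, rank 6) and the objection to the covariate would fall. But the two videos are the smoking and the neutral one, so varying them within arms would erase the difference between A and B and contradict the group definitions.

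A third is that adjustment may have been meant to remove the video difference between B and C when testing hypothesis (B). The design cannot do that: once video is held constant, only A versus C informs the group effect.

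It is also fair to say that the CO figures assume 20 separate occasions, which the plan does not state, and that hypotheses (A) to (C) concern craving rather than CO. The questionnaire figures carry the argument.

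**Conclusion.** The concern holds. As specified, video is an exact function of group and is the exposure in hypothesis (C). It contributes 0 df beside group, reduces a video-adjusted group test from 2 df to 1 (A versus C), and leaves A−B, B−C and pooled A+B versus C inestimable with video held constant. For group-by-time over the five questionnaire occasions, the result is 8, 7 or 4 df, depending on coding the plan does not give.

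This is an error of specification that costs no data, and it should be corrected before analysis. The conclusion rests on one assumption: that the group definitions, and not the randomised-video wording, describe what participants see. No power figure is attached, because the 1-df test can be more or less powerful than the 2-df test depending on the pattern of means.

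**What to change.** 1. Reconcile the randomised-video wording in At the research site and Craving Videos with the group definitions.
2. Remove the video term from the adjustment sentence. Fit group, time, group-by-time, sex and age.
3. Prespecify the contrasts: A−B for hypothesis (C), and A−C with B−C (or pooled A+B versus C) for hypothesis (B).
4. State what each contrast means. A−C isolates stimulation, under the smoking video only. B−C and pooled A+B versus C mix stimulation with video.

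An equivalent alternative to steps 2 and 3 is to replace the three-level group factor with two additive factors, stimulation (real or sham) and video (smoking or neutral), and to say that their interaction cannot be estimated. Either coding works, but not both together.

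The cost is two words deleted from one sentence, a short list of contrasts and a wording correction in two sections. Data collection and sample size do not change.

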These questionnaires will be administered to each participant prior to the first day of TMS treatment, after the last day of TMS treatment, after one week, after one month, and after six months. Participants will complete the questionnaires on a 14" laptop at baseline and first follow up, and then online during the remaining follow ups. The aim of the questionnaires will be to test for nicotine dependence, levels of craving, and screening for anxiety levels of participants at different time points. Those data will then be used for within and between participants' analyses. Further, participants will be asked through a visual analogue scale ranked from 1-100 "How much do you want to smoke right now?", prior and after each TMS session, as previously used by Revital Amiaz in similar methodology studies, to assess cue-induced craving of participants.

Smokerlyzer

Smokerlyzer is a non-invasive tool that measures the amount of CO on a smoker's breath and establishes smoking status biochemically. It will be used prior to each TMS session every day for each participant and its measures will be later used for analyses purposes.

Craving Videos

Two videos will be used during the TMS sessions, presented in a randomized manner. The first video is a smoking video which lasts for three minutes and its purpose is to be a cue for inducing craving. The other video used will be a neutral video, illustrating daily tasks that do not involve smoking. This video will be used as a control video.

TMS Protocol

This study will attempt to use accelerated theta burst stimulation of TMS, and specifically the 3-minute FDA-approved protocol for depression. rTMS will be applied to each participant for a period of five consecutive days. Each day will consist of four sessions of the 3-minute theta-burst stimulation with a 45-minute gap (which is the optimal gap) between sessions. The protocol includes 2 seconds of stimulation on the left dorsolateral prefrontal cortex which is followed by an 8 second pause. There will be 600 pulses in total for each 3-minute session. The site of stimulation will be the left DLPFC. It will be measured by using the 10-20 system, it will be determined by the Beam F3 software and it will be at 100% of the motor threshold.

Planned Analysis

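### The pre-treatment Fagerstrom score is collected from everyone but is not among the covariates for craving and CO, so a modest, avoidable loss of precision remains

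*Combined protocol and SAP*

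**What the plan says.** There is one document, a combined protocol and SAP.

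- **Adjustment (Planned Analysis):** "Analyses will be adjusted for sex, age and visual stimuli". No other covariate is named. The model is a repeated-measures mixed model in which baseline and follow-up scores form the within factor and the three groups form the between factor.
- **Dependence measure (Materials, Questionnaires):** the list opens with "The Fagerstrom Test of Nicotine Dependence (in Greek". On timing: "These questionnaires will be administered to each participant prior to the first day of TMS treatment". It is repeated after the last treatment day, at one week, at one month and at six months. The stated aim of the questionnaires is "to test for nicotine dependence, levels of craving, and screening for anxiety levels of participants at different time points", so the score enters the plan as a repeated outcome.
- **Other smoking history (Procedure, Prior to the study):** screening asks "how many cigarettes do you smoke per day". This is not used as a covariate either.
- **Allocation (Procedure, At the research site):** participants "will be assigned in a randomised manner to each defined group". No block, stratum or minimisation factor is described. The Participants section plans three groups of 34.
- **CO (At the research site; Smokerlyzer):** a reading is taken before each session on each treatment day.
- **Between-group hypothesis (B, end of Introduction):** groups A and B are expected to have lower craving than group C after treatment ends.

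**The concern.** Groups A and C watch the smoking video and group B the neutral one, so the visual-stimuli term is determined by group and carries no information about participants before treatment. That leaves sex and age.

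Entry requires tobacco dependence but sets no minimum Fagerstrom score or daily consumption, so the plan does nothing to narrow the spread of dependence. If dependence predicts later craving or CO beyond what the model already holds, leaving it out keeps explainable variance in the residual. It also lets a chance difference in dependence between arms of 34 shift the A–C, B–C and A–B estimates in the trial actually run. At stake are some precision and some protection against an unlucky allocation, obtainable from data already in hand.

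**Working it through.** **The plan's own figure.** There is none on this point. The sample size of 100 comes from an effect size of 0.4 with no stated power or metric, and it is not needed here.

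**Inputs.** From the documents: 34 per arm, 102 in total, five questionnaire visits. Assumed, because the documents give none: the correlations of Fagerstrom with baseline craving (a), Fagerstrom with later craving (b), and baseline with later craving (c).

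**1. Chance imbalance under unstratified allocation.** The standard error of a standardised baseline difference between two arms is √(2/34) = 0.243, so the 95% range is ±1.96 × 0.243 = ±0.48 SD. For a given pair, P(|difference| > t) = 2[1 − Φ(t/0.243)]. For the largest of the three pairwise differences I used 400,000 simulated sets of three arm means.

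| Difference exceeds | A given pair | At least one of three pairs |
|---|---|---|
| 0.25 SD | 30% | 56% |
| 0.3 SD | 22% | 43% |
| 0.5 SD | 4% | 10% |

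**2. What the planned model already removes.** Baseline is a level of the within factor. If dependence adds the same amount to craving at every visit, that amount cancels from a group-by-time contrast, which compares changes. Two things can remain: the part of dependence that predicts change, or the whole effect if the test compares post-treatment levels, as hypothesis B can be read. Planned Analysis does not say which contrast is tested.

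**3. Plausible partial correlation once baseline craving is accounted for.** r = (b − ac)/√[(1 − a²)(1 − c²)].

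- Mid-range case, a = 0.4, b = 0.3, c = 0.5: r = (0.3 − 0.2)/√(0.84 × 0.75) = 0.10/0.794 = 0.126, about 0.13.
- All 27 combinations of a = 0.3, 0.4, 0.5, b = 0.2, 0.3, 0.4 and c = 0.4, 0.5, 0.6: r runs from −0.14 to 0.32 with median 0.13. Two combinations reach 0.3, none reaches 0.4, and 18 fall below 0.2.

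**4. Gain from adjustment.** The standard error is multiplied by √(1 − r²). The equivalent extra participants are 102/(1 − r²) − 102. The last column is the approximate shift in the estimate, r × 0.3, in outcome SD, from an unadjusted 0.3 SD imbalance.

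| r | SE reduction | Extra participants | Shift |
|---|---|---|---|
| 0.13 | 0.8% | 1.8 | 0.04 |
| 0.2 | 2.0% | 4.3 | 0.06 |
| 0.3 | 4.6% | 10.1 | 0.09 |
| 0.4 | 8.3% | 19.4 | 0.12 |

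The 0.4 row lies outside the range found in step 3 and is shown only for scale.

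**5. Form of the covariate.** In a simulated trial of 102 participants at five visits with complete data, adding the covariate as a main effect left the group-by-time estimate unchanged (0.533 with and without it; SE 0.329 both times). Adding its interaction with time did change the estimate. A main effect alone therefore does nothing for a change contrast.

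**The case against.** The strongest case against is that this is an optional refinement, and much of it stands.

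- **No bias.** A reader might infer that the group comparisons are biased. They are not: randomisation keeps them unbiased on average, and ordinary standard errors already allow for chance imbalance. Imbalance and lost precision are one cost seen from two sides.
- **Baseline is not ignored.** A reader might infer that all of the effect of dependence is left in the estimates. The within factor contains baseline, so a change contrast removes the constant part.
- **The 43% is easily over-read.** It concerns the worst of three pairs at a modest threshold. At 0.5 SD it falls to 10%, and a 0.3 SD imbalance moves the estimate by only about 0.04 to 0.09 SD for r between 0.13 and 0.3.
- **Allocation.** A reader might infer that stratification by dependence was ruled out. The document gives one phrase on assignment, so stratification is undescribed, not excluded.
- **Prognostic value is assumed.** The Introduction links CO to blood nicotine, and blood nicotine to craving. It does not link the Fagerstrom score to either.
- **Blanket adjustment would be wrong.** Applying the score to every comparison would put Fagerstrom on both sides of its own model, and the first CO reading could end up the same way.

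These points limit the size of the gain and shape the remedy. They do not remove the point: a pre-treatment measure of the condition under study is available for everyone, is not in the stated covariate list, and can matter for a post-treatment comparison or wherever it predicts change.

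**Conclusion.** The point holds as a minor improvement in precision. The document confirms that dependence is measured in everyone before treatment, is absent from the adjustment set, and has no described role in allocation.

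Given baseline craving, the likely reduction in standard error is about 1%, and at most about 5% over the correlations tried. That is worth roughly 2 to 12 participants on 102 (at r = 0.13 and at the maximum of 0.32). The gain could be larger in a post-treatment level comparison that makes no use of baseline craving, where b rather than r applies. All of these sizes rest on assumed correlations. The grid was framed for craving; for CO the documents offer nothing from which to size the gain.

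The documents do not support calling the planned comparisons invalid or systematically biased.

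**What to change.** In Planned Analysis:

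1. Prespecify the pre-treatment Fagerstrom score as a continuous, centred covariate for the craving and CO comparisons, alongside sex and age. Use the pre-treatment value only, since later values may be affected by treatment.
2. If baseline stays a level of the within factor, include the interaction of the score with time. State which contrast tests hypothesis B, because that decides whether the interaction is needed.
3. Do not add the covariate where Fagerstrom is itself the outcome; its baseline is already in that model.
4. For CO, use the first day-1 reading either as one of the repeated responses or as a baseline covariate with only later readings as responses, not both.
5. Optionally, stratify allocation by Fagerstrom score with a cut-point set in advance, keeping the continuous score in the model. This requires the baseline questionnaires to be completed before allocation.

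**Cost:** no new data. One degree of freedom for the covariate alone, or about five with the time interaction over five visits (one for the main effect, four for the interaction). For CO the number depends on how the daily readings are grouped into time levels, which the plan should state. Stratification adds only a slightly longer allocation list.
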